10. DATA COLLECTION AND QUALITY ASSURANCE

10.1 Data Collection Forms

Research Assistants will screen and collect contact information for all study subjects on the “Participant Screening and Contacts Form”. Information will be collected by

Research Assistants over the telephone and entered directly into the electronic form. Forms are saved in a restricted research folder on secure VA networked computers.

Research Assistants will collect all baseline and follow-up interview data by telephone interview with the participants. They will enter data directly into REDCap questionnaires. Research assistants are blind to participant's randomization group. REDCap questionnaires and data are saved in VA REDCap and in a restricted research folder on secure VA networked computers. VA REDCap can only be accessed on the secure VA Network.

Electronic medical record data will be accessed and stored on the VA Informatics and Computing Infrastructure (VINCI) platform and in a restricted research folder on secure VA networked computers.

10.2 Data Management

VA REDCap is a secure web application for building and managing online surveys that can be used for direct data entry by Research Staff. Project questionnaires will be created and used for data collection. After data are collected, REDCap provides automated export procedures for data to be downloaded to Excel and common statistical packages (SPSS, SAS, R) for data analysis. In these programs, filters flag data that needs to be re-checked by a person such as unclear characters, out-of-range variables and logical inconsistencies. The project director and project statistician will check files monthly so that errors can be readily corrected and consequential differences between treatment types (e.g., different levels of attrition) can be monitored closely.

10.3 Quality Assurance

10.3.1 Training

Training of Study Counselors

[name] will provide competency-based supervision to support the counselors' delivery of SBIRT-PM throughout the trial. This approach is consistent with the national VA Evidence-Based Practice training model,⁹⁵ which emphasizes extended post-workshop case-based supervision or consultation, including submission of audio recorded therapy sessions for treatment fidelity review, as an essential training component. [name] will meet with the counselors together on a 1-hour monthly basis to review their SBIRT-PM practice. For these supervision meetings, he will listen to and rate the clinicians' SBIRT-PM fidelity for two sessions per counselor (one initial and one follow-up call) using the Independent Tape Rater Scale⁹⁶ for the purposes of feedback and coaching during supervision. In MI clinician training research, this approach and dose of supervision has been shown to sustain proficient practice.⁹⁷

The risk of angering or alienating Veterans is low because of the non-confrontational nature of SBIRT-PM. The risk will be further minimized by hiring experienced counselors who have experience with the study population. Study counselors will be trained to adopt a collaborative approach. Study counselors will also be knowledgeable about the location of emergency rooms, VA Police, and crisis

services available at each VISN1 medical center, as well as mandated reporting procedures for all sites.

Training of Study Research Assistant

Staff obtaining verbal consent will have completed a web-based course with post-test on Human Research Protections, and all will have had specific training by the mPIs in obtaining informed consent for this project.

The research assistant will receive training in the study assessments from the Project Director and the two mPIs. The research assistants will administer the study consent and assessments to other staff in role plays until they are administered correctly. Research assistants will be asked to contact the PIs about participant responses that are not obvious to code within the offered choice options.

The research assistant will also be knowledgeable about the emergency facilities (emergency rooms, VA Police, and crisis services) at each VISN1 medical center. The research assistant will also receive training in de-escalating agitated Veterans.

COVID-19 response: the research assistants collecting self-report data about pain and substance use service utilization will prompt veterans to consider in-person and all telehealth/virtual and telephone-delivered services when responding to our service utilization assessment.

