3. STUDY DESIGN

We will conduct a pragmatic two-arm, parallel groups 36-week multi-site randomized controlled single blind trial of SBIRT-PM. Drawing from VISN1 medical centers, we will randomize 1100 post-911 era Veterans applying for MSD-related compensation to either: 1) SBIRT-PM, a single phone-delivered session followed by up to three calls in a 12-week period and an additional call in the 12-32-week period; or 2) usual care (UC). Primary outcomes will be change in pain severity (BPI Composite severity) and change in the number of substances categorized as requiring intervention (ASSIST). The two primary outcomes will be measured by self-report at 12- and 36- week follow-ups. The self-report BPI and ASSIST measures will be completed with the Research Assistant by

telephone with the patient's responses entered directly into REDCap. The Research Assistant conducting all study assessments will be blinded. Secondary outcomes will include non-pharmacological pain management service utilization, pain interference with life activities (BPI), overall pain (PEG), overall health (EQ-5D-5L), use severity for individual substances generated by the ASSIST, and toxicology results for individual substances. The trial will include cost-effectiveness and budget impact analyses.

Study Settings.

The study will occur within the eight VISN1 VA medical centers (VAMC) located across six New England States. Each site provides MSD-related compensation examinations, addiction/mental health treatment, and a variety of non-pharmacological pain treatments.

The medical centers are:

1. Bedford VAMC
2. Boston Healthcare System
3. Central Western Massachusetts
4. Connecticut Healthcare System
5. Maine Healthcare System
6. Manchester VAMC
7. Providence VAMC
8. White River Junction VA

Feasibility of Recruiting a Sufficient Number of Veterans Who Meet Inclusion/Exclusion Criteria:

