- Characteristics of Musculoskeletal Disorders. We will determine the diagnostic group of MSD assigned to participants in the EHR by using ICD-9 or 10 codes. Major groups are back pain, neck pain, and osteoarthritis. Other categories will be combined as suggested by their frequency and co-occurrence with other MSD. These include non-traumatic joint disorders, osteoporosis, sprain and strain, traumatic joint disorder, spinal cord injury, fibromyalgia, rheumatoid arthritis, temporal mandibular disorder, lupus, gout, and MSD multimorbidity (more than one MSD diagnosed). The broad MSD groups will be considered as potential moderators of treatment effect in the analyses. In addition, compensation examiners complete a detailed, structured form, the Disability Benefits Questionnaire (DBQ), for each Veteran they evaluate. From these forms, we will extract structured notations of the examination findings. Finally, we will obtain the final percentage service-connection awarded from the Veterans Benefits Administration System (VBMS) after the determination, and delineate service-connected conditions.

Pain Measures:

- Brief Pain Inventory (BPI). The Brief Pain Inventory¹¹¹ (BPI) is a validated instrument to assess chronic non-cancer pain that yields two subscales. One measures pain severity (4 items on a 0-10 scale) and the other assesses pain interference with life activities (7 items on a 0-10 scale), both using a 24-hour recall period. BPI pain

severity will serve as our primary pain outcome for the trial; pain interference will serve as a secondary outcome. The BPI is a reliable measure and responsive to change.¹¹² The BPI is endorsed by the Initiative on Methods, Measurement, and Pain Assessment in Clinical Trials (IMMPACT) group¹¹³ as a preferred measure of pain-related functioning. IMMPACT recommendations have specified score changes that would represent a minimally clinically important difference (i.e., 30% reduction in pain severity and 1-point reduction in pain interference), which will be used in our cost analyses.¹¹⁴

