- ASSIST. Substance use will be measured over the last 3 months using Version 3.1 of the Alcohol, Smoking and Substance Involvement Screening Test (ASSIST). After a screening question focusing on substances ever used, the ASSIST consists of seven questions about use of and consequences of use of each of ten classes of substances over the preceding three months (including nicotine). Scores are generated for each substance that are mapped to a three-point ordinal scale of severity.¹¹⁹ As outlined in the World Health Organization's Manual describing the use of the ASSIST to guide treatment recommendations, the ASSIST ratings are scaled to represent no need for treatment, need for a brief intervention, and need for an intensive intervention. An advantage of the ASSIST is that these categories represent what clinicians consider a clinically important difference, in that they guide treatment recommendations. The items in the ASSIST have been shown to have good to excellent reliability for the substances assayed. The reliability of the individual ASSIST items,¹²⁰ and the ASSIST's concurrent validity compared to other more detailed assessments of substance use severity¹²¹ have justified its adoption by the World Health Organization.¹²² We will obtain additional specifiers for substances requiring further characterization: a specifier about use of vaping for tobacco products, a specification as to whether the Veteran is using legal or prescribed cannabis and specification about use of prescribed amphetamine.
- Prescription Opioid Misuse. Two questions,¹²³ adapted from the CIDI¹²⁴ for use in a NIDA Clinical Trials Network study,¹²⁵ will be used to describe misuse of prescribed opioid medications: *“How often have you taken your pain medications in larger amounts than prescribed or for a longer period than prescribed?”* and *“How often have you used your pain medicines to get high, to relax, or to make you feel more alert?”* The questions are asked about the preceding 4 weeks, with follow-up questions to clarify that the question refers to opioids only.

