- Relational Coordination Survey. This survey, will be administered post-trial to "hub" SBIRT-PM clinicians and "spoke" clinical and administrative staff in Compensation and Pension and Primary Care to examine how pain care was coordinated to meet the treatment needs of compensation-seeking Veterans. It includes seven dimensions: frequency of communication, timeliness of communication, accuracy of communication, problem-solving, shared goals, shared knowledge, mutual respect). Respondents indicate the frequency in which each dimension exists in their setting on a 5-point scale. The mean of the individual scores serves as the overall RC score for each dimension within each spoke site.
- Post-Trial Semi-Structured Qualitative Interview. At the end of the trial, we will conduct in-depth interviews with "hub" SBIRT clinicians and "spoke" clinical and administrative staff in Compensation and Pension and Primary Care to assess the organization and coordination of pain management services, given their experiences with SBIRT-PM implementation.

Randomization

The urn randomization covariates are: site (8 sites of VISN1), sex (M/F), race (White, Black, Other), ethnicity (Hispanic/Non-Hispanic), and self-reported illicit drug use (Yes/No). Following enrollment and Baseline assessments, the Project Director will enter covariates into urn randomization program to determine intervention condition assignment. Randomization will occur within two weeks of the enrollment date.

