6.2.3 Blinding

Research assistants who collect study data will be blind to participants' treatment assignment. Veterans will be instructed during the assessments not to tell the research assistant if they are receiving study counseling. To determine if the blind was maintained, the research assistant will be asked to what condition each Veteran was assigned. The PIs and Project Director will not be blind to randomization, as they will be assigning study therapists to participants randomized to the treatment condition, reviewing counseling sessions for quality/fidelity, and conducting monthly supervision with study counselors. The statistician has no contact with the study veterans; she will not be blinded.

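### Unclear follow-up answers are referred to unblinded PIs with no masking, so knowledge of arm can enter their coding, chiefly for ASSIST and service-use items

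*Combined protocol and SAP*

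**What the plan says.** Section 3 makes the interviewer the blinded party: "The Research Assistant conducting all study assessments will be blinded". The same section says of the outcomes: "The two primary outcomes will be measured by self-report at 12- and 36- week follow-ups". Answers are taken by telephone and entered directly into REDCap.

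Section 10.3.1, on training of research assistants, gives the rule for unclear answers: "Research assistants will be asked to contact the PIs about participant responses that are not obvious to code within the offered choice options". It names no instrument, visit or arm as exempt.

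Section 6.2.3, repeated under Blinding in section 9.2, says: "The PIs and Project Director will not be blind to randomization". The reasons given there are that this group assigns therapists, reviews counseling sessions and supervises counselors.

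Section 10.2 adds a second point of contact with the outcome data: "The project director and project statistician will check files monthly so that errors can be readily corrected". Section 6.2.3 says that neither the Project Director nor the statistician is blind.

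**The concern.** Participants know their arm: section 5.1 has the Project Director tell the usual-care group that they will get no study counseling. Since section 9.5.1 took toxicology out of the primary substance outcome, both co-primaries rest on self-report alone. The blinded interviewer is then the main documented safeguard in outcome assessment, and the answers that need judgement are the ones referred past that interviewer.

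What the PIs may know also differs by arm. Counseling sessions cover pain and substance use and exist only in the SBIRT-PM arm. A PI asked about an unclear answer may hold outside information on a counseled veteran that cannot exist for a usual-care veteran, even if everyone acts in good faith.

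The planned check on the blind would not show this. It asks the research assistant to guess the condition, and a guess at chance level says nothing about answers settled after a query to a PI.

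**Working it through.** **Which answers are exposed**

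- *Baseline.* Section 6.2.2 states: "Following enrollment and Baseline assessments, the Project Director will enter covariates into urn randomization program". No arm exists when baseline answers are given, and a query settled before randomization cannot be affected. The exposure is mainly at weeks 12 and 36.
- *BPI severity.* Section 6.2.2 describes the two subscales: "One measures pain severity (4 items on a 0-10 scale". A stated number leaves little to code.
- *ASSIST.* Section 6.2.2 says: "Scores are generated for each substance that are mapped to a three-point ordinal scale of severity". The primary outcome counts substances above the no-intervention threshold (9.5.1), so one recoded item can change a borderline count. Section 6.2.2 also says that some substances, such as cannabis and amphetamine, need extra specification.
- *Self-reported service use.* This secondary outcome asks about many treatment categories, with reason, setting, payer and frequency, and so invites coding questions.

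**The plan's own figures (section 9.2), reproduced**

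- Pain: n per arm = 2(2.2414 + 1.2816)² / 0.25² = 397.2, so 398 against the stated 400. Then 400 / 0.73 = 547.9, so 548 per arm and 1096 in total.
- Substance use, 27% vs 10%, two-sided 0.025, 90% power, no continuity correction: 128 per arm. Then 128 / 0.73 = 175.3, so 176 per arm and 352 in total.

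Both match, so 400 analyzed per arm at two-sided 0.025 is a fair base for the next step.

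**Scale of a possible effect**

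These inputs are assumptions and are not in the documents:
- f, the share of follow-up outcomes settled through a PI;
- s, the net between-arm shift in those outcomes on the BPI severity score, set at 1 point;
- q, the net share of referred ASSIST classifications moved across the threshold, set at one half;
- BPI SD of 1.5 to 2.0;
- all decisions leaning the same way by arm.

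The 10% rate for the ASSIST, treated as binary, is the plan's usual-care figure.

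Bias b = f × s for the BPI, or f × q for the ASSIST. SE = SD × √(2/400) for the BPI, or √(2 × 0.10 × 0.90 / 400) = 0.0212 for the ASSIST. Type I error = Φ(b/SE − 2.2414) + Φ(−b/SE − 2.2414).

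Example, ASSIST with f = 0.02: b = 0.02 × 0.5 = 0.01; b/SE = 0.471; Φ(−1.770) + Φ(−2.713) = 0.0384 + 0.0033 = 0.042.

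| Share referred, f | BPI type I error (SD 2.0 to 1.5) | ASSIST type I error |
|---|---|---|
| 1% | 0.0254 to 0.0256 | 0.029 |
| 2% | 0.0265 to 0.0276 | 0.042 |
| 5% | 0.034 to 0.042 | 0.144 |

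The nominal level is 0.025. The BPI column is generous: the score averages four items, so a 1-point shift through one queried item needs that item moved by 1 × 4 = 4 points. The share f counts referred outcomes, not interviews. Section 6.1 marks eleven self-report measures at each follow-up, so an interview with a query need not involve a co-primary. The planned ASSIST analysis is a count model, so the binary figures show order of magnitude only.

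**The case against.** The strongest reply is that section 10.3.1 says only that the PIs are contacted. It does not say that they score the answer. A PI could reply with a general coding rule, and nothing says that arm is ever mentioned. This stands as a limit on the claim: the documents show an open route, not a biased result. It does not close the route, because no section requires a general rule or a masked query, and the people contacted are stated to be unblinded.

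A reader might infer that the trial's single-blind description fails. The documents do not support that. They define the blind for the research assistants who collect the data, a query to a PI does not unblind the interviewer, and the PIs' knowledge of allocation is disclosed twice.

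A reader might also set a worst-case ASSIST bias beside the 6-percentage-point difference that section 9.2 calls detectable. That needs every referred case to cross the threshold in one direction by arm, at a referral share the documents do not give. It is not a fair measure of the threat.

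It could also be said that the sentence belongs to training. It sits under that heading, but it speaks of participants' responses, whereas the role plays described just before it are with other staff.

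Finally, section 9.5.1 already reports nail-sample return at week 36 among participants with completed ASSIST assessments. Follow-up data therefore exist, and a change to future queries alone cannot protect answers already coded. That is correct, and the remedy must look back as well.

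**Conclusion.** The point holds in limited form. The plan's stated procedure lets knowledge of arm reach the coding of unclear answers at weeks 12 and 36, mainly ASSIST items near the threshold and self-reported service use. BPI severity is little exposed, and baseline answers are largely unaffected.

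The size of any bias is unknown because no referral rate is given. Under the one-directional assumptions above, at 1% to 2% referral the effect on the BPI is negligible (type I error at most 0.028), while the ASSIST figure is 0.029 to 0.042. At 5% the ASSIST figure reaches 0.144. If decisions do not lean by arm, there is no systematic bias. This is a cheap gap to close, not a reason to doubt the blind as a whole.

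**What to change.** **For queries still to come.** Amend section 10.3.1 so that a coding query is written, gives the item and the answer without participant ID, site or arm, and is answered by a general rule applied to both arms. Alternatively, send it to someone blind to arm. Log each query by item, with the decision. Apply the same masking to corrections of outcome data under section 10.2, and to the matching monthly checks in section 10.3.5.

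**For answers already coded.** List any BPI or ASSIST items settled through a PI, as far as study records allow. Have an existing blinded team member recode them, or report a sensitivity analysis without them. If no record was kept, say so when reporting.

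**Cost.** A short operating procedure and slightly slower resolution of queries, plus a limited recoding exercise or one sensitivity analysis. No extra staff are needed, and N, alpha and power stay as planned.

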A research assistant, blind to study condition, will conduct baseline, 12- and 36-week participant assessments by telephone. Veterans will be instructed during the assessments not to tell the research assistant if they are receiving study counseling. To determine if the blind was maintained, the research assistant will be asked in what condition each Veteran was assigned. In the initial RCT of SBIRT-PM reported in the Preliminary Studies, the accuracy of research assistants' guesses about treatment condition assignment were almost exactly at chance (52%). We will abstract data from the VA electronic health record (EHR) when possible.

Procedures to Collect Self-Report Data from Veteran Participants.

The self-reported assessment will be conducted by phone. Baseline assessment will be conducted as soon as possible after enrollment, and follow-up phone assessments will be conducted approximately 12 and 36 weeks after randomization. Participants will receive a reminder call or text/email message prior to study appointments (e.g., "your follow-up phone interview with our research study is Monday, December 11th at 1:30. Please call [Name] at xxx-xxx-xxxx if you need to reschedule"). If a participant misses a scheduled appointment, the research assistant will call to reschedule. Participants will be asked at the beginning of enrollment for the names and telephone numbers of three

people who can find them if the research assistant has difficulty reaching them. These people will be contacted if the research team is unable to reach the Veteran within a three-week period.

Procedures to Collect Self-Report Data from VA Staff Participants

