6. STUDY PROCEDURES

6.1 Schedule of Evaluations

RCT Assessments

Assessment Name/Domain	Data Source	Baseline	12-wk	36-wk
Socio-demographic Characteristics	Self-Report	x		
Psychiatric and Substance Use Diagnoses	VA EHR -structured data (e.g. clinic codes)	x		
Characteristics of Musculoskeletal Disorders	VA EHR, Service-connection exam	x		
Distance to nearest VA Facility	VA EHR		x	
Brief Pain Inventory	Self-report	x	x	x
Numeric Rating Scale	Self-report	x	x	x
Opioid Medications Dispensed in Morphine Equivalent Daily Dose	VA EHR	x	x	x
Non-opioid Medications Dispensed	VA EHR	x	x	x
Non-pharmacological Pain Management Service Use—VA services	VA EHR -structured data (e.g. clinic codes)	x	x	x
Non-pharmacological Pain Management Service Use---VA and non-VA services	VA EHR with Natural Language Processing	x	x	x
Self-reported VA and non-VA service use	Self-report	x	x	x
ASSIST	Self-report	x	x	x
Prescription Opioid Misuse	Self-report	x	x	x
Nail clippings for drug/etoh use metabolites	Biological	x	x	x
Substance Use Treatment Service Utilization – VA services	VA EHR -workload data and clinic codes	x	x	x
Self-reported VA and non-VA substance use service use	Self-report	x	x	x
PHQ-9 (depression)	Self-report	x	x	x
EQ-5D -5L	Self-report	x	x	x
PEG	Self-report	x	x	x
Motivation for engaging in pain treatment	Self-report	x	x	x

High Impact Pain Questions	Self-report	x		
Audit-C	Self-report	x		
COVID-19 questionnaire	Self-report	x	x	x

UG3 Preparation Assessments and End-of-Study Assessments

Measures Described Earlier in UG3 Stage of RCT preparation	Data Source	UG3 preparation phase	End of Study
Qualitative Interviews of Stakeholders	Self-report	x	x
Post-intervention Interview of SBIRT-PM-treated Veterans	Self-report	x	
Relational Coordination Survey of Key Stakeholders	Self-report	x	x
Treatment Fidelity Measure: Independent Tape Rater Scale	audio recorded SBIRT-PM session ratings		x

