- Self-Reported Use of Pain Treatment Services. The PMC3’s phenotype and outcomes workgroup developed the “Use of nonpharmacological and self-care approaches” questionnaire to collect information about patients’ use of 13 different pain treatments, including Acupuncture, Rehabilitation Therapies, Manipulation, Massage, Yoga, Tai Chi/Qigong, Exercise, Biofeedback, Hypnosis/Hypnotherapy, Guided Imagery, Meditation, Psychotherapy/Counseling. In addition to asking about whether each treatment category was used, the instrument also includes questions about the most important reason for use, whether the treatment was received from a practitioner, the type of setting of use, how the service was paid for, how often it was used, and how effective it was in relieving pain. The instrument was modified for this study to collect information over the past 3 months (instead of past year), and to include several additional categories: Reiki, Pain School, Pain Clinic, primary care services, emergency/urgent care services, opiate and non-opiate medications.

Substance Use Measures:

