To reduce the risk that Veterans pass off someone else's fingernails as their own, they will be asked if the nails are theirs, and paid regardless of whether they are. Specimen substitution when there are contingencies for positive urines occurs, but there is no incentive for such false reporting when payment is provided regardless of the sample results. The samples will be mailed in coded envelopes addressed to our group, further reducing the likelihood of submitting someone else's fingernails.

- Samples will be processed at the United States Drug Testing Laboratories (Illinois). After processing, samples will be destroyed following a standard storage period. Sample analysis uses fully validated methods that have been inspected and approved by the College of American Pathologists Forensic Drug Testing Program and the New York State Department of Health. Substance Use Treatment Service Utilization-VA Records. Visits from the EHR involving substance use treatment will be identified conservatively, using an algorithm involving workload information entered at clinic visits (e.g. diagnosis treated, procedure performed) and the type of clinic providing the treatment. The measure does not capture much substance abuse counseling in primary care settings, and in conjunction with other mental health treatment (i.e., PTSD treatment). For this reason, self-reported substance use service utilization will be collected (see below).
- Self-Reported Use of Substance Use Treatment Services: Using the same format as the pain treatment service use questions described above, we will inquire about *whether* each of a number of classes of treatments was received in the preceding 12 weeks (substance use counseling, day program, residential, ER/hospital, self-help, counseling at a medical visit, counseling at a visit for a psychiatric condition, opioid substitution, smoking cessation counseling, nicotine replacement therapy prescribed).

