7.2 Methods and Timing for Assessing, Recording, and Analyzing Safety Parameters

Unanticipated problems will be recorded as they are discovered throughout the study. The Project Director will record all reportable events with start dates occurring any time after informed consent is obtained until the last day of study participation (approximately 36 weeks after baseline). At each study visit (Baseline, week 12, week 36), the study team will inquire about the occurrence of AE/SAEs since the last visit.

Our group completed a randomized controlled trial of 101 participants to a face-to-face version of SBIRT-PM or two control conditions in a very similar population to that

proposed in this application ([name] et al., 2018). There were no study-related adverse events in that study, and they are unlikely in this study as well.

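### The service-use prompt covers all telephone-delivered services without excepting the study's own telephone counseling, and no rule keeps SBIRT-PM contacts out of the service-use outcome and mediators

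*Combined protocol and SAP*

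**What the plan says.** Section 10.3.1 (Training, COVID-19 response) directs that the assistants who collect self-reported pain and substance use service data "will prompt veterans to consider in-person and all telehealth/virtual and telephone-delivered services when responding to our service utilization assessment". Sections 6.2.3 and 10.1 make those assistants blind to arm. The intervention is itself telephone counseling on pain and risky substance use (section 5.1).

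Section 6.2.3 also states that "Veterans will be instructed during the assessments not to tell the research assistant if they are receiving study counseling"; sections 3 and 9.2 repeat this. As a check, "To determine if the blind was maintained, the research assistant will be asked to what condition each Veteran was assigned".

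Several items could take in a study call:

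- The pain questionnaire in section 6.2.2 has a psychotherapy/counseling category with a 3-month recall, and asks "whether the treatment was received from a practitioner, the type of setting of use, how the service was paid for, how often it was used".
- The substance use questionnaire in the same section covers the preceding 12 weeks and asks about "substance use counseling, day program, residential, ER/hospital, self-help, counseling at a medical visit", among others, and about smoking cessation counseling.
- The modality sum in section 9.5.2 includes teaching about coping with pain and an open category for other treatment.

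Section 9.6 (Analyses of NLP Algorithms) counts a modality as used if self-report, stop codes or NLP shows it, and expects false positives to be unlikely. It does not discuss study counseling. Service use is a secondary outcome (section 9.5.2) and a mediator under Objectives 1 and 2 (section 1.1).

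**The concern.** Veterans in the SBIRT-PM arm are asked to think of every telephone service and, in the same interview, not to mention one of them. The plan does not say how the two instructions fit together, or whether a study call is a service for scoring purposes.

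Two things are at stake. The first is measurement. A Veteran who counts the calls can add a pain modality or a substance use service that no usual-care Veteran can add from the same source. The utilization outcome then partly records delivery of the intervention, and the mediator partly restates treatment assignment. The plan already treats SBIRT-PM participation (yes/no) as a separate potential mediator (sections 5.4 and 9.6), so the two would be blurred. Error in the other direction is also possible: a cautious SBIRT-PM Veteran may hold back genuine outside counseling.

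The second is the blind. Both primary outcomes are now interviewer-administered self-report, since section 9.5.1 takes nail toxicology out of the substance use primary. A Veteran who describes study calls may reveal the arm to the assessor.

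**Working it through.** The plan gives no figure on this point, so there is none to reproduce. What follows shows how the possible error scales.

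**Inputs**

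- Share of the SBIRT-PM arm counseled: 80% (pilot, section 10.3.5).
- Evaluable Veterans per arm: 400 (section 9.2). Check: 2 × (2.241 + 1.282)² / 0.25² = 397.2, so 398, close to the stated 400.
- f, the share of counseled Veterans who report study calls as a service: an assumption. No document gives a value.
- SD of the modality count: assumed 1 to 2.
- Two-sided alpha 0.05: assumed for a secondary outcome.

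**Spurious difference in the modality count.** If each such report adds one category and the arms do not otherwise differ, the difference is 0.80 × f. It is smaller where the Veteran already counts in that category.

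**Chance of a significant difference from this alone.** With k = 0.8f / (SD × √(2/400)), the chance is Φ(k − 1.96) + Φ(−k − 1.96).

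| f | 0.8f | SD 1 | SD 2 |
|---|---|---|---|
| 0% | 0 | 5% (alpha) | 5% (alpha) |
| 10% | 0.08 | 20% | 8% |
| 25% | 0.20 | 81% | 29% |
| 50% | 0.40 | about 100% | 81% |

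**Blind.** Suppose every such report gave the arm away, which is a worst case. Guess accuracy would be 0.5 × [0.8f + 0.5(1 − 0.8f)] + 0.5 × 0.5 = 0.5 + 0.2f if all other guesses are random, and 0.5 × 0.8f + 0.5 = 0.5 + 0.4f if all others are guessed as usual care. That is 52–54% at f = 10%, 55–60% at 25% and 60–70% at 50%.

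**Which visit.** A 3-month recall at week 12 covers roughly weeks 0 to 12, the main counseling period. At week 36 it reaches back to about week 24 (36 − 12), so mainly the single optional call in weeks 12 to 32 (section 5.1) could be caught, and only if it falls late in that period.

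**Mapping.** The questionnaire's counseling category does not appear by name in the list summed in section 9.5.2. A study call could enter through the coping-teaching or other-treatment categories, but the plan does not state how the questionnaire items map to the sum.

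**The case against.** The strongest reply is that the non-disclosure instruction already acts as an exclusion. It is given during these same assessments, and a Veteran can satisfy both instructions by reporting every other telephone service. This largely stands: the instructions are unreconciled on paper but not incompatible, and at f = 0 both self-report effects vanish. It remains an instruction about disclosure, however, and does not define what counts as a service.

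A reader might go further and infer that the prompt draws out treatment arm. The documents do not support that. Section 5.1 says VA telehealth expanded during the pandemic and that usual-care Veterans are reminded to pursue any counseling they need, so telephone counseling can be reported in either arm. The same applies to a headcount such as 0.8 × 0.30 × 550 = 132 Veterans unmasked. It equates a report with unmasking, rests on an assumed f, and ignores the planned 27% attrition (0.24 × 400 = 96).

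A reader might also take the schedule in section 6.1, where "Self-reported VA and non-VA service use" is listed ahead of the ASSIST, to mean that the arm is exposed before a primary outcome is taken. That table is a schedule of assessments, not an interview sequence, and it lists the BPI before service use.

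Other safeguards exist. The assessor's guess is recorded, assistants are trained by role play and consult the investigators on responses that are hard to code (section 10.3.1), and the Précis says outcomes will be corroborated with the health record and toxicology. The full interview script is not reproduced, so it may contain an exception that the protocol does not show. These points lower the concern without closing it. The guess can detect unblinding but does not prevent it. The 52% accuracy cited in section 3 is from the initial trial, apparently the face-to-face one ("Our group completed a randomized controlled trial of 101 participants to a face-to-face version of SBIRT-PM or two control conditions"), so it does not test a prompt about telephone services.

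**Conclusion.** The point holds as a gap in wording and scoring. The prompt makes no exception for study calls, it is not reconciled with the non-disclosure instruction, and no rule keeps SBIRT-PM contacts out of a measure that serves as both secondary outcome and mediator. Any resulting inflation falls in one arm only and mainly at week 12.

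Its size cannot be determined from the documents. It is up to 0.8f modalities, given 80% counseled and one added category per report, and zero under full compliance with the non-disclosure instruction. Risk to the blind likewise depends on compliance; it is not an established result of the prompt. The definitions of the primary outcomes, the sample size and the power are unaffected. This is an inexpensive improvement that bears mostly on how the utilization and mediation results can be read.

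**What to change.** 1. For remaining interviews, read the same prompt in both arms: include telephone and video services, but leave out any counseling calls that are part of this research study. Complete the BPI and ASSIST before the service-use items.
2. State in sections 9.5.2 and 9.6 that SBIRT-PM contacts are not counted as service use from self-report, stop codes or NLP. All three need naming because counselors also place session notes in the health record (section 5.2), so a self-report fix alone may not be enough.
3. Section 9.5.1 already reports week-12 and week-36 nail-return rates, so many interviews are evidently done. For these, do not delete reports by matching them to counselor contact logs. The logs exist for one arm only, so genuine outside counseling could be removed from SBIRT-PM alone, biasing the comparison against it. Instead, repeat the utilization and mediation analyses in both arms without the self-reported counseling, coping-teaching and other-treatment items that could absorb study calls, and report these beside the main results.

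The cost is one script sentence, a fixed form order, one scoring rule and one sensitivity analysis. The drawback is that some genuine counseling is left out of the sensitivity analysis, by the same rule in both arms.
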